4.1.2 ASP7517 Monotherapy Arm in Dose Escalation Phase 1 Cohort

For ASP7517 Monotherapy Arm in Dose Escalation portion participants will receive 1 dose of ASP7517 on Day 1 of each 28-day cycle for up to 6 doses. Following the first 2 cycles, participants who have not met any individual treatment discontinuation criteria and are receiving clinical benefit (defined as radiological response or stable disease [SD], or reduction of disease-related symptoms) may continue further treatment with ASP7517, as decided by the investigator.

Participants who achieve confirmed complete response (CR) within the first 4 cycles will not receive further treatment with ASP7517, and participants who achieve partial response (PR) or SD after 4 doses may receive an additional 2 doses. An EOT visit will be conducted for all participants within 7 days of EOT determination or prior to the initiation of new anticancer therapy, whichever occurs first.

The starting dose level is 1×10^7 cells/dose and the decision to escalate to the next dose level (1×10^8 cells/dose) will be made based on the assessment of safety variables, including the occurrence of dose limiting toxicities (DLTs). Dose level may be de-escalated to a lower dose level (1×10^6 cells/dose) based on the occurrence of DLTs.

After the EOT visit, participants will complete 30-day, 60-day and 90-day safety follow-up visits from the last dose of ASP7517 or prior to the initiation of new anticancer therapy.

All participants will enter an observation period except those with confirmed disease progression by immune response evaluation criteria in solid tumors (iRECIST) (iCPD), unconfirmed disease progression based on iRECIST (iUPD) (per independent central review or local review) and who are not clinically stable or clinical progression is confirmed by the investigator. Participants in the Monotherapy Arm Observation Period will be followed for up to 48 weeks starting at EOT until iCPD per independent central review, initiation of a new

anticancer therapy or meeting 1 of the Observation Period discontinuation criteria, whichever occurs first. Safety Follow-up period is included in Observation Period.

All participants will be followed for survival, subsequent anticancer treatments and treatment outcomes following the conclusion of the Observation Period.

Refer to [Section 4.1.5] for additional dose escalation cohort management details.

4.1.3 ASP7517 and Pembrolizumab Combination Therapy Arm in Dose Escalation Phase 1 Cohort

In the combination treatment arm, ASP7517 will be given on Day 1 of each 28-day cycle for up to 6 doses in combination with pembrolizumab for up to 4 doses administered every 6 weeks, starting from Day 1 of Cycle 1. For combination treatment, a 400 mg pembrolizumab infusion will be administered first, followed by an ASP7517 infusion at least 1 hour after the completion of the pembrolizumab infusion. Following the first 2 cycles, participants who have not met any individual treatment discontinuation criteria and are receiving clinical benefit (defined as radiological response or SD, or reduction of disease-related symptoms) will continue further treatment with ASP7517 and pembrolizumab as decided by the investigator. Participants who achieve confirmed CR within the first 4 cycles will not receive further treatment with ASP7517 at Cycle 5 and Cycle 6 (end of Treatment period) and participants who achieve PR or SD after 4 doses may receive additional 2 doses of ASP7517 in combination with pembrolizumab.

Participants completing the Treatment period who enter the Observation Period with CR, PR or SD are allowed to continue on pembrolizumab alone up to a total of 17 doses for those participants who, in the opinion of the investigator, are continuing to derive clinical benefit.

Subsequent to the Treatment period, all participants, except those with iCPD, iUPD who are not clinically stable or have clinical disease progression per independent central review or local review will enter the Observation Period to monitor treatment response. Participants in the Combination Arm Observation Period will be followed for up to 78 weeks starting at EOT until iCPD (confirmed by independent central review or local review), initiation of a new anticancer therapy or meeting 1 of the Observation Period discontinuation criteria, whichever occurs first. If participant discontinues combination treatment of ASP7517 at any time prior to C5D15, then the participant should continue observation period up to a total of 96 weeks.

After discontinuation of IP, all participants will complete an EOT visit, along with 30-, 60- and 90-day safety follow-up visits from the last dose of IP or prior to the initiation of new anticancer treatment.

The initial dose escalation cohort of pembrolizumab combination with ASP7517 will use a starting dose of ASP7517 1×10^7 cells/dose.

The decision to escalate to the next dose level (1×10^8 cells/dose) will be made based on the assessment of safety variables, including the occurrence of DLTs. A dose level of ASP7517 may be de-escalated to a lower dose level (1×10^6 cells/dose) based on the occurrence of

DLTs. Refer to [Section 10.1.5.1 Dose Escalation and Safety Committee] for details about the DESC.

All participants will be followed for survival, subsequent anticancer treatments and treatment outcomes following the conclusion of the Observation Period.

4.1.4 Dose Limiting Toxicity Criteria

A DLT is defined as any of the following events that occur within 28 days starting with the first dose on Cycle 1 Day 1 (C1D1) and that is considered to be related to IP. Confirmation of DLTs will be made by the DESC. The severity of AEs will be assessed according to the National Cancer Institute's Common Terminology Criteria for Adverse Events (NCI-CTCAE), version 5.0.

4.1.4.1 ASP7517 Monotherapy Arm DLTs

- Non-hematologic AEs that are \geq grade 3 and that do not resolve to \leq grade 2 within 72 hours of onset
- Confirmed Hy's law case
- IRR that requires the infusion to be discontinued
- Prolonged delay (> 2 weeks) in initiating Cycle 2 due to treatment-related toxicity
- Any treatment-related toxicity that causes the participant to discontinue treatment during Cycle 1
- Grade ≥ 3 thrombocytopenia accompanied by bleeding that requires transfusion or hospitalization
- Grade ≥ 3 anemia requiring transfusion
- Grade 3 febrile neutropenia with or without infection
- Grade 5 treatment-related toxicity

The following AEs will not be considered as DLTs in the ASP7517 monotherapy arm:

- Electrolyte abnormalities that are not associated with clinical sequelae or deemed not clinically significant and corrected with appropriate management or supplementation within 72 hours of onset
- Grade 3 infusion site reaction if successfully managed and resolved within 72 hours
- Alopecia, anorexia or fatigue
- Grade 3 nausea and/or vomiting if not requiring tube feeding or total parenteral nutrition, or diarrhea and/or constipation if not requiring or prolonging hospitalization that can be managed to grade ≤ 2 with standard antiemetic or antidiarrheal medications used at prescribed dose within 72 hours of onset
- Grade 3 liver function test (LFT) elevations that resolve to \leq grade 1 within 7 days; LFT elevations lasting > 7 days that are considered to be clinically significant and at least possibly related to ASP7517 will be considered to be a DLT
- Grade 3 irAEs that resolve to \leq grade 1 within 72 hours of onset

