AE: adverse event; DLT: dose limiting toxicity; ECG: electrocardiogram; ECOG: Eastern Cooperative Oncology Group; IFN γ : interferon gamma; iRECIST: immune response evaluation criteria in solid tumors; MTD: maximum tolerated dose; NK: natural killer; NKT: natural killer T; RECIST: response evaluation criteria in solid tumors; RP2D: recommended phase 2 dose; SAE: serious adverse event; WT1: Wilms' tumor protein 1.	
Study Population: Participants with locally progressive (unresectable) or metastatic solid tumor malignancies known to express Wilms' tumor protein 1 (WT1) antigen (including but not limited to melanoma, ovarian cancer and colorectal cancer [CRC] who have received all standard therapies except checkpoint inhibitor [CPI]-naïve melanoma in phase 2).	
Number of Participants: Approximately 385 participants may be enrolled. Phase 1 (Dose Escalation Cohort): Approximately 24 participants may be enrolled in the escalation cohorts (approximately 12 participants for monotherapy and 12 participants for combination therapy). Phase 2 (Dose Expansion Cohort): The total number of participants in the expansion cohorts will depend on the observed antitumor activity. It is estimated that approximately 361 participants may be enrolled in the monotherapy and combination therapy arms (approximately 129 participants for monotherapy and 232 participants for combination therapy).	
Study Design Overview: This study is a phase 1/2, open-label study of ASP7517 as monotherapy and in combination with pembrolizumab in selected participants with advanced solid tumors known to express WT1 antigen.	

This study consists of arms receiving ASP7517 monotherapy and arms receiving ASP7517 and pembrolizumab combination therapy in phase 1 (dose escalation cohort) and phase 2 (dose expansion cohort). Phase 2 monotherapy and combination dose expansion cohorts will be opened after the phase 1 dose escalation has been completed for the monotherapy and the combination therapy, independently.

In this study, 28 days will define each cycle during Cycles 1 to 6.

Additional cohort may be added by a protocol amendment to further evaluate ASP7517 as a single agent and/or in combination with another anti-cancer agent.

ASP7517 Monotherapy Arm

This arm will consist of Screening (up to 28 days); Treatment (up to 6 doses); End of Treatment (EOT) visit; Safety follow-up (30, 60 and 90 days); Observation Period (up to 48 weeks); and Survival follow-up (up to 12 months).

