A Dose Escalation and Safety Committee (DESC) consisting of sponsor representatives and investigators will convene once a dose level cohort completes the DLT observation period and data are available for review. Additional details regarding responsibilities, membership requirements and safety review time points are included in the DESC Charter. The DESC will also review the aggregate safety data from the phase 1 dose escalation and phase 2 expansion cohorts.

While safety data from the DLT observation period in the escalation cohorts are the minimum safety data needed for the DESC meeting, all available safety findings will be considered by the DESC. The DESC will assess whether a longer DLT observation period is warranted based on emerging data. Additionally, only when determining the RP2D, the DESC may choose a more conservative dosing decision than the maximum tolerated dose (MTD) selected by BOIN design, based on evaluation of the safety data and other available data.

The decision on the dose level for the next cohort will be based on the BOIN design. In addition, MTD will be determined by BOIN from at least 6 participants. The dose for phase 2 expansion will not be higher than the MTD.

Participant Replacement during Dose Escalation Cohort

Participants may be replaced in the dose escalation cohort if:

- Participant is discovered to have enrolled without fully satisfying eligibility criteria
- Participant received less than the planned dose in Cycle 1 for reasons other than DLT
- Participant has no DLT and withdraws from the study before the end of DLT evaluation period

The decision regarding replacement of individual participants will be made by the sponsor with discussions with the treating investigator. Participants who experience DLTs in the dose escalation cohort will not be replaced.

Dose evaluation and dose escalation stopping rules based on the BOIN design with target DLT rate of 0.30 and optimal interval of (0.236, 0.359) are as follows:

Action	Number of Participants Treated at Current Dose Level					
	3	4	5	6	7	8
Escalate dose if number of participants with DLT \leq	0	0	1	1	1	1
Stay at current dose level if number of participants with DLT =	1	1	-	2	2	2
De-escalate if number of participants with DLT =	2	2	2 or 3	3	3 or 4	3 or 4
Stop if number of participants with DLT \geq	3	3	4	4	5	5

DLT: dose limiting toxicity

Dose escalation within individual participants will not be allowed.

Maximum Tolerated Dose

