2.3.2 Risk Mitigation

The study population is restricted to participants with advanced/metastatic solid tumors who have received, declined or had a contraindication to all therapy with established clinical benefit for their malignancy. Strict adherence to the eligibility criteria is essential to ensure investigators select appropriate participants for participation in the study.

Additionally, the following precautions mitigate risk and protect participant safety:

- Conservative criteria for interruption and/or discontinuation of study treatment.
- The Dose Escalation and Safety Committee (DESC) will convene once a dose level cohort completes the dose limiting toxicity (DLT) observation period and the data are available for review. The committee's decision on the dose level for the next cohort will be guided according to the Bayesian optimal interval (BOIN) Design based on DLTs observed in the DLT observation period. While safety data from the DLT observation period in the escalation cohorts are the minimum safety data needed for the committee meeting, all available safety findings, including those occurring after the designated DLT observation period that meet DLT criteria ("delayed DLT"), will be considered by the committee.
- The safety in the expansion cohorts will be monitored using Bayesian logistic model and based on all DLT data obtained up to that time from both escalation cohorts and expansion cohorts and drug-related treatment-emergent adverse events (TEAEs) leading to death. Safety monitoring with these models will be started when an expansion cohort is opened. Enrollment in expansion cohorts may be held based on the criteria described in Section 9.5.

The potential risk of irAEs and infusion-related reactions (IRRs) may be mitigated by closely monitoring participants' symptoms, signs and clinical laboratory test results to facilitate early identification and management, as per the guidelines in Section 10.8 Appendix 8: Infusion Reaction Dose Modification and Treatment (Guidelines for ASP7517 and Pembrolizumab); Section 10.9 Appendix 9: Monitoring of Pembrolizumab Potential Immune-related Adverse Events; Section 10.10 Appendix 10: Dose Modification and Toxicity Management for

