The MTD determination will be based on at least 6 evaluable participants at that dose level based on the BOPIN design. Based on the observed DLT(s) during the DLT observation period, the MTD is the highest dose for which the isotonic estimate of the DLT rate is closest to, but not over, the target DLT rate of 0.30 for monotherapy and combination therapy.

The dose level determined to be the MTD must have data from at least 6 participants. Determination of MTD will be done for monotherapy and combination therapy separately.

Recommended Phase 2 Dose

The sponsor, in conjunction with the DESC, will determine the RP2D of ASP7517 as a single agent and in combination with pembrolizumab taking into consideration the safety and efficacy data, as well as other available data, such as pharmacokinetics and pharmacodynamics of ASP7517. The RP2D will not exceed the MTD.

The dose level determined to be the RP2D must have data from at least 6 participants. Determination of RP2D will be done for monotherapy and combination therapy separately.

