5.2.1.1 Dose-Limiting Toxicity (DLT)

A DLT is defined as any of the listed events that occur within 28 days starting with the first dose on cycle 1 day 1 (C1D1) and that is considered to be related to IP. Confirmation of DLTs will be made by the DESC. The severity of AEs will be assessed according to the

National Cancer Institute's Common Terminology Criteria for Adverse Events (NCI-CTCAE).

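### Two DLT rules miscount if read literally: in both arms a Cycle 2 delay of more than 2 weeks cannot fall inside the 28-day DLT window, and the monotherapy febrile neutropenia bullet omits Grade 4 (minor)

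*Protocol*

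**What the plan says.** **The window.** Protocol 4.1.4 limits DLTs to "any of the following events that occur within 28 days starting with the first dose" on Cycle 1 Day 1 and judged related to investigational product. SAP 5.2.1.1 repeats it: "A DLT is defined as any of the listed events that occur within 28 days starting with the first dose". The Synopsis states that "28 days will define each cycle during Cycles 1 to 6".

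**The delay bullet.** Protocol 4.1.4.1 (monotherapy) and 4.1.4.2 (combination) both list "Prolonged delay (> 2 weeks) in initiating Cycle 2 due to treatment-related toxicity". The Synopsis repeats both lists.

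**What feeds the decisions.** Protocol 2.3.2 guides the next dose by the BOIN "Design based on DLTs observed in the DLT observation period". For the MTD, Protocol 4.1.5.2 says: "Based on the observed DLT(s) during the DLT observation period, the MTD is the highest dose" that meets the target criterion. The DLT tabulation in SAP 6.5.2 is confined to the same period.

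**The committee's latitude.** The DESC confirms DLTs (4.1.4). Under 2.3.2 it considers "all available safety findings, including those occurring after the designated DLT observation period that meet DLT criteria". The Synopsis adds: "The DESC will assess whether a longer DLT observation period is warranted based on emerging data". It also says that the next cohort's dose follows BOIN, and that the DESC may be more conservative than the BOIN MTD only when setting the RP2D.

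**Febrile neutropenia.** The monotherapy list names Grade 3 only. The combination list says Grade 3 or higher and defines Grade 4 separately.

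**The concern.** A delay in starting Cycle 2 cannot begin until Cycle 2 is due, which is after the 28-day window has closed. A criterion that the protocol means to be dose-limiting therefore has no moment at which it can be satisfied. The DESC convenes once the cohort has finished the DLT period, and no rule stops it from counting a participant whose Cycle 2 is on hold as DLT-free.

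The bullet is not redundant. Section 6.5 bars the next ASP7517 dose until a related grade 3 event has resolved to grade 1. A related grade 3 non-hematologic event that falls to grade 2 within 72 hours escapes the first DLT bullet but can still hold Cycle 2 for weeks. Prolonged afebrile neutropenia, or thrombocytopenia without bleeding, also meets no other bullet unless it ends treatment in Cycle 1.

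For febrile neutropenia, what is literally omitted is a related, nonfatal Grade 4 case. Two other rules depend on such a case being a DLT: no Cycle 2 after a grade 4 DLT, and the pause after grade 4 or higher DLTs in two participants.

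At stake are the BOIN count in cohorts of 3 to 8, the MTD estimate, and the DLT data carried into phase 2 safety monitoring (9.5).

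**Working it through.** **1. Timing.** Inputs: the DLT window is Days 1–28 (4.1.4), the cycle is 28 days (Synopsis), and the delay must exceed 14 days (4.1.4.1, 4.1.4.2).
- Cycle 2 is due on Day 1 + 28 = Day 29.
- A delay of exactly 14 days ends on Day 29 + 14 = Day 43, so a longer delay first exists on Day 44.
- Gap after the window closes: 44 − 28 = 16 days. With the ±1 day visit window for Cycle 2 Day 1 (Tables 1 and 2), the day is 43 to 45 and the gap 15 to 17 days.

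**2. The plan's BOIN figures.** Target φ = 0.30. Assume the multipliers 0.6 and 1.4, so φ₁ = 0.18 and φ₂ = 0.42.
- λₑ = ln(0.82/0.70) / ln[(0.30 × 0.82)/(0.18 × 0.70)] = 0.2365
- λ_d = ln(0.70/0.58) / ln[(0.42 × 0.70)/(0.30 × 0.58)] = 0.3585

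These agree with the stated interval (0.236, 0.359). With a stop rule of P(rate > 0.30) > 0.95 under a Beta(1,1) prior, every tabulated action for n = 3 to 8 is reproduced. The table itself is sound.

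**3. What one missed DLT does.** Section 4.1.5.2 plans 3 or 4 evaluable participants, then 3 or 4 more, so n is 3, 4, 6, 7 or 8.

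| True count | Tabulated action | Count with one missed | Tabulated action |
|---|---|---|---|
| 1/3 | stay | 0/3 | escalate |
| 1/4 | stay | 0/4 | escalate |
| 2/6 | stay | 1/6 | escalate |
| 2/7 | stay | 1/7 | escalate |
| 2/8 | stay | 1/8 | escalate |

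This matters below 1×10⁸. At 1×10⁸ there is no higher dose, so in these cells only the MTD estimate moves. Before any isotonic pooling, 2/6 = 0.333 is over the 0.30 target and 1/6 = 0.167 is not. By contrast, 2/7 = 0.286 and 2/8 = 0.25 are under it with or without the missed event.

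**4. Illustration only.** Let p be the true DLT rate and s the share of DLTs left uncounted. Both are assumptions; the documents give neither. The counted rate is q = p(1 − s). The escalation probability is (1 − q)³ at n = 3 and P(Bin(6, q) ≤ 1) at n = 6, treating n = 6 as a single look.

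| n | p | s = 0 | 5% | 10% | 20% |
|---|---|---|---|---|---|
| 3 | 0.20 | 0.512 | 0.531 | 0.551 | 0.593 |
| 3 | 0.30 | 0.343 | 0.366 | 0.389 | 0.439 |
| 3 | 0.40 | 0.216 | 0.238 | 0.262 | 0.314 |
| 6 | 0.20 | 0.655 | 0.680 | 0.704 | 0.753 |
| 6 | 0.30 | 0.420 | 0.453 | 0.487 | 0.558 |
| 6 | 0.40 | 0.233 | 0.266 | 0.301 | 0.378 |

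The rise is about 2 to 7 percentage points for s = 5% to 10%, and about 8 to 15 points for s = 20%.

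**5. Febrile neutropenia.** Under 7.3.1 events are relisted at each grade change, so a Grade 4 case that passes through a recorded Grade 3 inside the window is captured. Grade 5, and any related toxicity that ends treatment in Cycle 1, have their own bullets. A site that classed the event as non-hematologic could also use the 72-hour bullet. What remains is a related, nonfatal Grade 4 case with no Grade 3 entry in the window that does not end treatment in Cycle 1.

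**The case against.** The ordinary reading is that the toxicity must arise on Days 1–28 and the delay is its consequence; otherwise the bullet would be pointless. Section 4.1.4.2 supports that intent: under its heading on DLTs that require discontinuation, it lists a Cycle 2 delay of more than 4 weeks, which also falls after Day 28. This stands as evidence of intent, but no sentence states it. Even on that reading, nothing says when a participant on hold may be counted as DLT-free.

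A reader might infer that these toxicities have no route into the BOIN count. The documents do not support that. The DESC confirms every DLT, considers late events that meet the criteria, and may lengthen the window. The escalation text also refers to safety variables beyond DLTs. The route exists but is discretionary. The DESC Charter, which is not available here, may say more.

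A reader might also look to n = 5, where the table would move from de-escalate at 2/5 to escalate at 1/5. The planned cohort sizes do not produce n = 5.

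On febrile neutropenia, the combination list defines Grade 4 as the Grade 3 criteria plus life-threatening consequences, and the monotherapy exclusions do not exempt it. A DESC would very probably count it. That makes it a drafting slip, but one in a safety rule.

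The SAP records that the study closed early, which limits the practical value of a change. The documents do not say whether escalation had finished.

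**Conclusion.** Wrong as written, and minor. The mismatch is certain on the text: in both arms the delay criterion cannot occur inside its own window, and the monotherapy febrile neutropenia bullet is narrower than evidently intended.

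The size is a judgement, not a computed result. Calling it small rests on the overlap with other bullets (most liver toxicity has its own criteria), on the DESC's latitude, and on how few cases fall through every other rule. The first-in-human study reported no DLTs, and its 11 febrile neutropenia SAEs were assessed as unrelated with no grade given. It is a different study and does not estimate the share of uncounted DLTs here. The effect is small in likelihood rather than in consequence, since a single missed event can change an action in a cohort of this size.

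A reader might go further and infer that escalation was unsafe or the MTD biased. Nothing in the documents shows that such an event occurred or went uncounted.

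**What to change.** 1. In the Synopsis and Protocol 4.1.4.1 and 4.1.4.2, replace the delay bullet with: *Treatment-related toxicity with onset on Days 1–28 that delays the start of Cycle 2 by more than 2 weeks.*
2. In the BOIN and DESC text (Synopsis and 2.3.2), state that a participant whose Cycle 2 is held for related toxicity is not counted as DLT-free for BOIN until Cycle 2 starts or the delay passes 2 weeks.
3. Match the wording in SAP 5.2.1.1 and the DLT summary line in SAP 6.5.2. SAP 5.2.1.2 and 5.2.1.3 already defer to the protocol.
4. In the Synopsis and Protocol 4.1.4.1, change Grade 3 to Grade ≥ 3 in the monotherapy febrile neutropenia bullet.

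A separate DESC classification for participants who leave while on hold is not needed to cure this defect. The cost is wording, plus a wait of up to about 16 days (Day 28 to Day 44) only when a participant's Cycle 2 is on hold for toxicity. Sample size and BOIN boundaries do not change. Given the early closure, the remaining use is consistent DLT reporting and any reuse of this text.
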